Young people enroll by texting "DITCHVAPE" to a short code and responding to the initial message with their age and first name (used for tailoring the program). Terms of Service and Privacy Policy are provided via a link in a text message. Users receive one age-appropriate message per day tailored to their enrollment date or quit date, which can be set and reset via text message. Those not ready to quit receive 4 weeks of messages focused on building skills and confidence. Those who set a quit date receive messages for a week before and 8 weeks afterward that include encouragement and support, skill- and self-efficacy building exercises, coping strategies, and information about the risks of vaping, benefits of quitting, and cutting down to quit. Keywords COPE, STRESS, SLIP, and MORE provide on-demand support. Sample text messages can be found at the end of this protocol. Users can unsubscribe by texting STOP. E-cigarette use and abstinence are assessed via text message at 14, 30, 60, and 90 days following an enrollee's quit date or enrollment date. At 14 days, enrollees are asked, "Have you cut down how much you vape in the past 2 weeks? Respond w/letter: A=I still vape the same amount, B=I vape less, C=I don't JUUL at all anymore." At 30, 60, and 90 days, enrollees are asked, "When was the last time you vaped, even a puff of someone else's? Respond w/ letter: A: in the past 7 days, B: 8–30 days ago, C: More than 30 days ago."

As of July 27, 2021, over 350,000 young people have enrolled, including over 130,000 adolescents aged 13-17, demonstrating the appeal of this treatment approach and the urgent need for quit vaping resources

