among young people. Preliminary evaluation data collected among an initial cohort of roughly 27,000 users has shown high levels of engagement in the program and high rates of abstinence among responders. Roughly ¾ of users set a quit date, with the most common quit date being the day of enrollment. Interactive keywords were used by 45.5% of teens and 38.4% of YA. Response rates to follow-up assessment questions were 36.9% at 14 days and 21.0% at 90 days. At 14 days, 60.8% of respondents indicated they had reduced or stopped using e-cigarettes altogether. At 90 days, 7-day point prevalence abstinence (ppa) was 25% and 30-day ppa was 16%. The high volume of enrollment in a short period of time, high levels of engagement with the program, and e-cigarette reduction and cessation results demonstrate that young people are interested in quitting vaping and can be engaged in an easily accessible, anonymous digital platform.

We recently completed an evaluation of This is Quitting with 2,588 young adults aged 18-24. Under an intention-to-treat analysis with missingness coded as vaping, abstinence rates were 24.1% among participants assigned to the intervention (This is Quitting) and 18.6% among participants in the assessment only control arm, a statistically significant difference (Odds Ratio=1.39, 95% CI 1.15-1.68, p< 0.001). [10]

Building on previous research, the primary aim of the current study is to conduct a comparative effectiveness trial to evaluate the effectiveness of *This is Quitting* in promoting abstinence from e-cigarettes among adolescents aged 13-17. This study is a 2-arm randomized controlled trial conducted among young users aged 13-17 recruited through online channels. Participants will be randomized to *This is Quitting* or an assessment-only control condition and followed for 7 months to roughly correspond to 6-months post-treatment. The secondary aim is to examine potential mediators of program effectiveness, including treatment engagement and changes in self-efficacy and perceived social support for quitting.

We will also include a waitlist control arm to evaluate the influence of assessment reactivity and retention incentives given relatively high quit rates among assessment-only control participants in the previous YA trial and the dearth of data on adolescent vaping cessation. This arm was not included in sample size calculations.

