Assessment-only control: After an initial enrollment message, participants will be contacted monthly to assess e-cigarette use. At the end of the study, participants will receive information about how to sign up for This is Quitting if they are interested.

Waitlist control: After an initial enrollment message, participants will only be contacted at 1 and 7 months to complete the follow-up assessments; there will be no other contact via text message. At the end of the study, participants will receive information about how to sign up for This is Quitting if they are interested.

Potential Problems and Solutions

Loss to follow-up is the primary concern in trials involving digital interventions, especially ones that employ an assessment only or minimal contact controls. For the treatment and assessment only control arms, we expect at least 75% follow-up at 1-month and 65% at 7-months based on our previous and ongoing digital mobile-based evaluations. If follow-up rates are lower than expected early in the trial, we will consider shortening the 7-month follow-up to gather only abstinence outcomes.

To maximize follow up rates we will:

- 1) provide clear information about the study at the outset, including expectations for follow-up;
- 2) reimburse participants up to \$30 per follow-up assessment;
- 3) collect interim abstinence assessments via text ("Retention Messages": \$5 incentive for each response) for intervention and assessment-only control arms;
- 4) send reminders about follow-up surveys via email and text messages;
- 5) conduct phone follow-ups for those unreachable by email and text messages;
- 6) contact participants via social media private messaging function (if permission given); and,
- 7) emphasize the importance of survey completion regardless of abstinence status.

Conducting research online involving incentives carries the potential for fraud and participant deception as there are often no direct interactions with the participants.¹¹ To prevent fraudulent enrollments and participation from bots, we will utilize the following features on the Qualtrics survey platform:

- 1) Prevent multiple submission: Enabling this option allows Qualtrics to place a cookie on the browser the first time someone takes the survey. The user will be flagged as duplicate if they come back to take the survey from the same browser and device without having cleared their cookies.

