- 2) Bot detection: Enabling bot detection flags responses that are likely completed by bots by assigning a score to each response. This feature uses Google's invisible reCaptcha technology to assign a score to each response, with a score of less than 0.5 meaning that the respondent is likely a bot.
- 3) Relevant ID: This feature analyzes a user's browser, operating system, and location to calculate a fraud score that indicates whether the respondent is attempting to take the survey multiple times.

We also require a valid email address for completion of the baseline survey (users must click on a survey link in their email to launch the baseline and complete enrollment), which has been shown to prevent bots. ¹² We will monitor emails and phone numbers used to enroll in the study on a daily basis and exclude any duplicates. We anticipate these measures will prevent the majority of any potentially fraudulent enrollments.

Measures

All randomized participants in both arms will be asked to complete all assessments. Assessments will occur at baseline and 1 month and 7 months post-randomization. The baseline survey will be conducted online and hosted on a secure server. Mixed-mode follow-up (email, phone, text) will be employed. Telephone surveys will be conducted by research staff blind to treatment. Text messages have demonstrated moderately high reliability (k=.66) compared with web-based surveys in assessing smoking outcomes¹³ and will be used as a final means of gathering abstinence data from non-responders. Most measures listed below are standard instruments used in cessation studies, and are reliable when administered via the Internet. ^{14,15}

Screening Variables. Individuals located outside the U.S. (as determined by IP address captured by the survey platform) will be ineligible to participate. To characterize the sample of users interested in the study and assess study eligibility, we will gather: demographics (age, education, income level, sexual and gender identity, race, and ethnicity); current e-cigarette use (use of e-cigarette containing nicotine or THC in the past 30 days)¹⁶; interest in quitting; contact information (e-mail and phone number to send baseline survey to and link text message sign-up data). These questions are being asked during screening so we can determine whether enrolled participants are representative of the wider population of e-cigarette users.

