Missing Data. Missing data will be handled in two ways. First, we will conduct an intent-to-treat (ITT) analysis in which participants who have been lost to follow up are assumed to be treatment failures (i.e., vaping). This analysis will be conducted because ITT analyses are common in the smoking cessation literature, despite simulations demonstrating that the approach is neither conservative nor anti-conservative but rather biased in favor of whichever condition contains less missingness. Second, we will supplement the ITT analyses with an analysis that uses a multiple imputation (MI) procedure to minimize bias in estimates and standard errors, under the assumption that outcomes are not missing at random (NMAR) but rather more likely to be missing for treatment failures (i.e., vaping) than treatment successes (i.e. abstinence). Since the magnitude of actual response bias is unknown, we will conduct a sensitivity analysis to evaluate the treatment effect on outcomes under a range of magnitudes, from equal odds of missing (OR=1) to five times more likely to be missing (OR=5).

Mediator Analysis. Our conceptual model is that treatment increases the odds of abstinence by increasing perceived social support and perceived self-efficacy for quitting. Those two constructs will be measured at baseline, 1-month and 7-months post-treatment. Change in those constructs from baseline will be evaluated with separate mediation analyses as presented in Figure 1. Specifically, we hypothesize that the effect of treatment on abstinence will be mediated by perceived social support and perceived self-efficacy, such that: (1) a significant effect A is found associating X with Z; (2) a significant effect B is found associating Z with Y; (3) a significant effect C is found associating X with Y; and (4) the effect of C is significantly attenuated when A and B are simultaneously included in the model.

PROTECTION OF HUMAN SUBJECTS

Human Subjects Involvement, Characteristics, and Design

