There is no payment for study enrollment or completion of the baseline assessment. All participants are asked to complete follow-up surveys at 1- month and 7-months post-randomization. Participants will be paid \$20 for completing each follow-up survey via the Internet or by phone with a telephone interviewer. Participants who respond within 24 hours of receiving the initial survey invitation will receive an additional \$10. Participants in the intervention and assessment-only control arms will also be compensated \$5 for each text message assessment (7 total) they respond to, for a total compensation of up to \$95 for their entire study participation. Payment for completing the surveys and the text message assessments will be delivered via Rybbon, a company specializing in digital gift management for marketing and research. Rybbon is fully integrated with Qualtrics. When a participant completes an assessment, Rybbon will generate a unique link for gift card redemption and will email it to the participant. Rybbon has no access to any other identifying information other than email and no access to assessment data. Participants can redeem their Rybbon gift card from a variety of gift card options.

IMPORTANCE OF THE KNOWLEDGE TO BE GAINED

This is Quitting is the first text message intervention for e-cigarette cessation designed specifically for young people. We have seen a high volume of enrollment since the program launched in January 2019 with only earned media and organic marketing efforts to date. We have been flooded with interest from youth-serving organizations looking for a proven quit vaping program to offer to their young people. To our knowledge, this study will be the first to rigorously evaluate a scalable, cost-efficient, market-tested quit vaping program among adolescents. These data are urgently needed.

DATA AND SAFETY MONITORING PLAN / DATA & SAFETY MONITORING BOARD

Confidentiality will be protected at all times and potential risks will be minimized systematically. The following measures will be taken specifically to ensure data safety and monitoring.

Youth Advisory Board

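### The not-missing-at-random sensitivity analysis uses one response-bias range (OR 1 to 5) and makes no provision for bias that differs by arm; a two-way grid would be a cheap improvement

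*Combined protocol and SAP*

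**What the plan says.** The Missing Data paragraph of the Data Analysis Plan sets out two analyses. The first counts everyone lost to follow-up as vaping; the plan itself warns that this is "biased in favor of whichever condition contains less missingness". The second is multiple imputation that assumes vapers are more likely than abstainers to be missing. The strength of that bias is not known, so a sweep is planned: "we will conduct a sensitivity analysis to evaluate the treatment effect on outcomes under a range of magnitudes, from equal odds of missing (OR=1"). At the upper end of the sweep, a vaper is taken to be "five times more likely to be missing (OR=5"). One range is given. The text neither requires the OR to be equal in the two arms nor provides for it to differ.

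On the amount of missing data, Potential Problems and Solutions states: "we expect at least 75% follow-up at 1-month and 65% at 7-months". Up to about 35% of primary outcomes may therefore be absent.

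**The concern.** Response bias here means that, within an arm, vapers are less likely to answer than abstainers. Suppose its strength is the same in both arms and follow-up is similar. Both abstinence rates then fall together as the assumed OR rises, and the treatment OR hardly changes. Missing=vaping is the limit of the same model as the OR grows without bound, so it adds no different test. On that reading neither planned analysis examines bias that is stronger in one arm than in the other.

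Unequal bias is possible because only one main arm receives a quitting program, and a participant who is still vaping may be more or less willing to report it to the people who ran that program. What is at stake is the robustness claim: a five-fold sweep that barely moves the estimate could be reported as strong reassurance although this form of bias was never varied.

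**Working it through.** **Inputs.**
- Missing=vaping abstinence in the earlier young-adult trial (introductory section): "abstinence rates were 24.1% among participants assigned to the intervention (This is Quitting) and 18.6% among participants in the assessment only control arm". Using these rates for adolescents is an assumption.
- 900 per main arm (Subjects).
- 7-month follow-up of 65%, the plan's expected minimum, assumed equal in the two arms.
- Two-sided 5% level and no covariate adjustment (assumptions).

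**The documents' own figure first.** Odds are 0.241/0.759 = 0.3175 and 0.186/0.814 = 0.2285, a ratio of 1.39, as reported. Splitting the 2,588 participants equally (1,294 per arm, an assumption) also returns the reported interval, 1.15 to 1.68. At 900 per arm the same rates give 1.39 (1.11 to 1.74).

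**Model.** Let f be the follow-up proportion, p the responders' abstinence rate and k the OR for a vaper rather than an abstainer being missing.
- p = missing=vaping rate / f: 0.241/0.65 = 37.1% and 0.186/0.65 = 28.6%.
- Odds of abstinence among the missing = [p/(1−p)]/k, which gives p_m.
- Overall rate T = f·p + (1−f)·p_m.
- Variance by Rubin's rules with many imputations: within = T(1−T)/900; between = (1−f)²·[(dp_m/dp)²·p(1−p)/n_resp + p_m(1−p_m)/n_miss].
- Variance of the log OR = the sum over arms of (within + between)/[T(1−T)]².

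**One cell worked: This is Quitting k=2, control k=1.** Responder odds are 0.3708/0.6292 = 0.589. Halved, they are 0.295, so p_m = 22.8% and T = 0.241 + 0.35 × 0.228 = 32.1%. Control T = 28.6%. OR = (0.321/0.679)/(0.286/0.714) = 1.18 (0.92 to 1.50), p = 0.19.

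**Common k.** At k=1 the rates are 37.1% vs 28.6%, OR 1.47 (1.15 to 1.88), p = 0.002. At k=5 they are 27.8% vs 21.2%, OR 1.43 (1.13 to 1.81), p = 0.003.

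**Separate k by arm** (treatment OR; * marks a 95% CI that includes 1):

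| This is Quitting k | Control 1 | Control 2 | Control 3 | Control 4 | Control 5 |
|---|---|---|---|---|---|
| 1 | 1.47 | 1.82 | 2.00 | 2.12 | 2.19 |
| 2 | 1.18* | 1.46 | 1.60 | 1.69 | 1.75 |
| 3 | 1.06* | 1.32 | 1.45 | 1.53 | 1.58 |
| 4 | 1.00* | 1.24* | 1.36 | 1.44 | 1.49 |
| 5 | 0.96* | 1.19* | 1.31 | 1.38 | 1.43 |

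The extreme corners are 0.96 (0.76 to 1.22) and 2.19 (1.72 to 2.79). Six cells lose significance, and in each the This is Quitting k is at least twice the control k. No cell with the This is Quitting k at or below the control k does so. Simulated multiple imputation with 20,000 draws agrees: cell (5,1) gives 0.96, p = 0.74; cell (4,2) gives 1.24, p = 0.079; cell (5,3) gives 1.31, p = 0.027.

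**Varying the assumptions.**
- Follow-up of 65, 70, 75 and 80% in both arms: 6, 6, 5 and 4 non-significant cells.
- Control missing=vaping rate of 10, 15, 18.6, 25 and 30%, with that OR held at 1.39 and 65% follow-up: 8, 6, 6, 6 and 5 cells. At 10% the two extra cells are (3,2) and (5,3).

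**Where the planned range does respond.** With follow-up of 70% for This is Quitting and 60% for control, and the missing=vaping rates unchanged, a common k of 1 to 5 gives p = 0.21, 0.078, 0.043, 0.029 and 0.022.

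**The case against.** The plan is already better than many. It warns about missing=vaping, adds imputation under an explicit not-missing-at-random assumption and fixes a range in advance. The text does not impose a common OR, so a version by arm is not excluded. The common range also responds to unequal follow-up, which is the bias the plan names. All of this stands, and it is why the point is an improvement only.

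The design also limits unequal bias. On the paid text assessments, seven in each main arm, the payment section says: "Participants in the intervention and assessment-only control arms will also be compensated" for each reply. Survey payments and follow-up effort are the same in both main arms. "Telephone surveys will be conducted by research staff blind to treatment", although the phone is only one of the follow-up modes. "Those who set a quit date receive messages for a week before and 8 weeks afterward", so program contact normally ends well before month 7. These features make a large difference less likely; they do not show that it is zero.

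Two further points are fair. The at-least-twice boundary belongs to the base illustration: it shifts with the inputs, for example at 75% follow-up or a 10% control rate. And if the imputation uses baseline predictors, 1-month data or the text assessments, which the plan does not state, the result could be less sensitive to the OR than shown. Neither point supplies a test of unequal bias.

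**Conclusion.** The point holds as a modest, worthwhile improvement. The plan gives one range and makes no provision for ORs that differ by arm. With similar follow-up and a common OR, the planned sweep is nearly flat (1.47 to 1.43), so it cannot show how much between-arm difference the conclusion would survive. In the base illustration a contrast of 2 against 1 is enough to lose significance, yet 19 of 25 cells keep it, and bias that is stronger in the control arm only strengthens the result.

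These figures illustrate sensitivity and do not forecast the trial. They rest on young-adult rates applied to adolescents, equal 65% follow-up, no covariate adjustment and imputation from arm and response alone. The two corner cells are extremes, and nothing in the documents says that they are likely.

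**What to change.** Keep both planned analyses. Add to the Missing Data paragraph that the same imputation will also be run with the response-bias OR set to 1, 2, 3, 4 and 5 separately in This is Quitting and in the assessment-only control. Report all 25 cells and mark those whose 95% CI includes 1. The diagonal of the grid is the common-OR analysis, so this also settles how the present wording is to be read.

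The cost is about 25 imputation runs instead of about 5, and one more table. No new data are needed. The robustness statement may become less favourable than a common-OR sweep alone would allow.

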Baseline Variables. To characterize the sample and explore potential moderators of treatment effectiveness, we will gather: additional demographics (student status, employment status); current ecigarette use and history (frequency and rate, 16,17 age of first use, motivation to quit and quitting history 18); nicotine dependence will be assessed with the Penn State Electronic Cigarette Dependence Index 19, EDS/PROMISE-E, 20 the Hooked on Nicotine Checklist, 21 and the E-cigarette Fagerström Test of Cigarette Dependence (e-FTCD) 22; other substance use (other tobacco products, alcohol) and mental health symptoms 23; and adverse childhood events. 24,25 For co-morbidities and adverse childhood events, we chose measures that are validated for use among adolescents. In order to minimize risk to participants, we deliberately avoided measures or deleted questions that assessed sensitive topics such as suicidality. Given evolving trends of e-cigarette use and perception, we will also ask about perception about harm from e-cigarettes, reasons for wanting to quit, and reasons for joining the study. To account for potential predictors of dropout, we will ask about motivation to use or quit e-cigarettes and potential barriers to quitting (e.g., social influences). We will assess baseline levels of perceived level of social support, 26,27 perceived social norms, and perceived self-efficacy for quitting and examine changes in these variables as potential mediators of treatment effectiveness.

Mediating Variables. We hypothesize that treatment engagement will mediate the relationship between treatment assignment and abstinence outcomes. We will extract data regarding replies to interactive text messages (e.g., setting a quit date, keyword use) as well as unsubscribe status, number of days enrolled, and total number of messages received. All text message interactions are date/time stamped.

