Outcome Measures. The primary outcome is self-reported 30-day point-prevalence abstinence (ppa) at 7-months but we will gather abstinence data at all follow-ups. Other quitting-related outcomes include change in motivation to quit, quit attempts, reduction in e-cigarette use, 7-day ppa, and continuous abstinence measured at each follow-up. Intervention satisfaction in both conditions will be measured with items about overall satisfaction and whether they would recommend it to a friend (scale from 0-10). Satisfaction with frequency of text messages will be measured.²⁸ To assess perceived message relevance, participants will be asked whether text messages "were written personally for you"²⁹ and "were directed at you personally".³⁰

Data Analysis Plan

[figure not shown]
Primary Analysis. Point-prevalence abstinence (ppa) at 7-months post-randomization will be compared across the treatment and control groups using logistic regression. All estimates will be adjusted for baseline confounders of the intervention-outcome relationship. We will identify potential moderators (e.g., age, gender, baseline motivation to quit) by analyzing interactions between treatment and selected variables. For

all moderators found to be associated with the primary outcome, we will examine the effects of treatment/moderator interaction terms on outcomes after entering main effects.

Secondary Analyses. Additional outcomes related to abstinence and treatment engagement will also be analyzed with logistic regression as secondary analyses. These include likelihood of making a quit attempt, likelihood of reducing e-cigarette use, and changes in confidence and self-efficacy in quitting e-cigarettes.

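### The mediation plan takes change from baseline as the mediator and does not say that the baseline score enters the models; if it is left out, effect B is generally biased.

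*Combined protocol and SAP*

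**What the plan says.** All places are in the combined protocol and SAP.

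- **Form of the mediator.** Data Analysis Plan, Mediator Analysis: "Change in those constructs from baseline will be evaluated with separate mediation analyses as presented in Figure 1". Measures, Baseline Variables, likewise intends to "examine changes in these variables as potential mediators of treatment effectiveness". The secondary aim in the introduction is also framed in terms of changes in self-efficacy and social support.
- **Timing.** "Those two constructs will be measured at baseline, 1-month and 7-months post-treatment". A baseline score is therefore on file for each participant who completed the survey.
- **Decision rule.** Mediation is claimed if four conditions hold. They include "a significant effect A is found associating X with Z", "a significant effect B is found associating Z with Y", and that "the effect of C is significantly attenuated when A and B are simultaneously included in the model". These conditions name only X, Z and Y.
- **Covariates.** The one covariate rule is under Primary Analysis: "All estimates will be adjusted for baseline confounders of the intervention-outcome relationship". It does not mention confounders of the mediator-outcome relation.
- **Not visible.** Figure 1, to which the mediation sentence refers, is not reproduced in the available text.

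**The concern.** Randomisation protects effect A, the treatment contrast in the mediator. It does not protect effect B, the association of the mediator with abstinence within arms. A change score is usually correlated negatively with its own baseline, because those who start high tend to rise less. Baseline confidence or support may also predict quitting in its own right. A model with treatment and change but no baseline score therefore forces a restriction: the baseline score must act on abstinence with the same strength as the follow-up score and the opposite sign. The plan neither states nor justifies that restriction.

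The secondary aim is at stake. Significance of B is one of the four conditions, so an attenuated B can lead to a real mechanism being reported as absent. If the point stays open, two models with quite different power also remain available after the data are seen.

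**Working it through.** **Plan's own figure.** There is none. The documents give no effect size, SD, baseline to follow-up correlation, alpha or power for the mediation analysis.

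**Inputs from the documents.** 1,800 participants, 900 per main arm (Subjects). Expected follow-up of at least 75% at 1 month and 65% at 7 months (Potential Problems and Solutions), giving 0.75 x 1,800 = 1,350 and 0.65 x 1,800 = 1,170. Control abstinence of 18.6%, from the earlier young-adult trial (introduction).

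**Assumptions.** Correlation r of 0.3 to 0.7; ratio k of follow-up SD to baseline SD of 0.8 to 1.25; effect A of 0.2 SD (0.18 in one run); effect of follow-up level 0.3 to 0.8 log-odds per baseline SD; direct treatment effect 0.2 log-odds; two-sided 5% tests.

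**Step 1: closed form.** Let the log-odds of abstinence be b1 x follow-up + b0 x baseline, plus treatment. The within-arm least-squares slope on D = follow-up minus baseline is

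[b1(s1² - r·s0·s1) + b0(r·s0·s1 - s0²)] / (s0² + s1² - 2r·s0·s1).

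Its difference from b1 is (b1 + b0)(r·s0·s1 - s0²) divided by the same denominator. This is zero if b0 = -b1, or in the coincidental case r·k = 1, where change is uncorrelated with baseline. In the assumed range r·k is at most 0.7 x 1.25 = 0.875, so that case does not arise.

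**Step 2: equal SDs.** The slope is (b1 - b0)/2 for any r below 1. With b1 = 0.3:

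- b0 = 0 gives 0.15.
- b0 = 0.15 gives 0.075.
- b0 = 0.3 gives 0.
- b0 = -0.15 gives 0.225.
- b0 = -0.3 gives 0.3, which is no bias.

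**Step 3: unequal SDs, b0 = 0.** The factor on b1 is (k² - rk)/(1 + k² - 2rk). For example, k = 0.8 and r = 0.7 gives (0.64 - 0.56)/(1.64 - 1.12) = 0.08/0.52 = 0.15.

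| r | k = 0.8 | k = 1 | k = 1.25 |
|---|---|---|---|
| 0.3 | 0.35 | 0.50 | 0.66 |
| 0.5 | 0.29 | 0.50 | 0.71 |
| 0.7 | 0.15 | 0.50 | 0.85 |

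**Step 4: logistic check.** Simulated data sets of 200,000 gave factors of 0.46 to 0.49 with equal SDs. Effect A was recovered without bias. With b1 = 0.5, B was 0.24 to 0.25 without the baseline score and about 0.50 with it. The indirect effect was 0.048 to 0.049 against about 0.100.

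**Step 5: trial-size check.** n = 1,170, 500 runs, equal SDs, b0 = 0, b1 = 0.3. Entries are the percentage significant, without then with the baseline score in both models.

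| r | A | B | A and B |
|---|---|---|---|
| 0.3 | 80 → 92 | 70 → 97 | 56 → 89 |
| 0.5 | 95 → 98 | 52 → 95 | 50 → 93 |
| 0.7 | 99 → 100 | 34 → 85 | 34 → 84 |

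With b1 = 0.5 the joint figures are 81 → 94, 85 → 97 and 72 → 100. A separate run with n = 1,350 and A = 0.18 SD, b1 = 0.3, gave 61 → 93, 54 → 93 and 36 → 87.

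**Step 6: cost if change really is what matters.** With equal SDs and b0 = -b1, adding baseline multiplies the standard error of B by about √(2/(1 + r)): 1.24, 1.15 and 1.08 at r = 0.3, 0.5 and 0.7. It multiplies the standard error of A by √((1 + r)/2): 0.81, 0.87 and 0.92. The two roughly offset. In simulation with b1 = 0.3 and b0 = -0.3 the joint figure was 90% without baseline and 93% with it.

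**The case against.** **The omission is inferred from silence.** The model is deferred to a figure that is not available, and change from baseline could describe a baseline-adjusted analysis. This stands. A reader might infer that the plan excludes the baseline score, but the documents do not say so.

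**A covariate rule exists.** It does, but it sits under Primary Analysis and concerns the intervention-outcome relation. Baseline self-efficacy matters here as a confounder of the mediator-outcome relation, which the rule does not clearly reach.

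**Change is the stated quantity of interest.** The conceptual model is that "treatment increases the odds of abstinence by increasing perceived social support and perceived self-efficacy for quitting". If abstinence depends purely on change, there is no bias. That is correct, and the documents do not choose between level and change. But the quoted sentence describes what treatment does to the constructs, and it fits either model. The recommended model does not require a choice.

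**Halving is too definite.** A reader might infer that the indirect effect is understated by half or more. The documents do not support that: it needs equal SDs and a baseline effect that is zero or favours abstinence. With an SD ratio of 1.25 and no baseline effect the loss is 15% to 34%. With a baseline effect of minus half the follow-up effect and equal SDs it is 25%.

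**The power contrast is not the plan's rule.** This also stands. The rule also requires a significant C and a significant attenuation of C, which were not simulated. Part of the gain is ordinary precision in A: at r = 0.3, A alone moves from 80% to 92%. At r = 0.7, A is near 100% either way and almost all of the gap comes from B.

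**Conclusion.** The point holds in conditional form. The plan makes change from baseline the mediator and does not state that the baseline score enters the models. If it does not, B and the indirect effect are biased, except where baseline and follow-up act with equal and opposite strength (or in the coincidental case in step 1). If abstinence depends on the level reached, B is about half its true value with equal SDs, and about 0.15 to 0.85 of it over the assumed ranges. It is lower still if a higher baseline score independently favours abstinence. The loss in the chance of meeting the A and B conditions together can be large at b1 = 0.3 and is smaller at b1 = 0.5.

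The SDs, correlations and effect sizes are all assumptions, so the actual size in this trial cannot be determined from the documents. The point concerns a secondary aim only and leaves the primary treatment comparison untouched. It is best treated as a free improvement.

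**What to change.** Add one sentence to Mediator Analysis: for each construct, its baseline score is a covariate in the mediator model (effect A) and in the abstinence model that contains treatment and mediator (effect B and the attenuated C). The unattenuated C should be fitted with the same covariate, so that the attenuation step compares like with like. If Figure 1 already shows this, say so in the text. Apply the same rule to perceived social norms if that construct is analysed, since Baseline Variables lists it with the others.

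With the baseline score in the model, the change score and the follow-up score give the same B, and the pure change model remains a special case. The cost is one sentence. The scores are already collected, no participant contact changes, and step 6 shows little loss if pure change is the truth. The adjustment does not remove other confounding between mediator and abstinence.
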